5.2 Informed Consent Procedures

Summary of HIPAA and Consenting Requests:

Phase 1:

- ***Gain perspective of PACT providers, staff, and Veterans on how pain screening information should be collected and how screening can be integrated with informatics: HIPAA authorization not necessary for VA staff participation. Verbal consent was obtained, and a waiver of documentation of consent was approved. HIPAA authorization forms would have been used for Veteran participants. However, there were none.***

Phase 2:

- ***Multisite RCT to test pain screening approaches via tablet, Patient follow-up interviews, Provider interviews:*** Waiver of Documentation of Consent necessary. HIPAA authorization is not necessary for the provider interviews. A HIPAA authorization form will be filled out and signed by patient participants. Research staff will mail a copy of the signed HIPAA form to the participant.

Local site study personnel will be trained regarding human subjects protections requirements and how to obtain verbal consent. Study personnel are required to be up to date in the mandatory security and patient confidentiality trainings. Additionally site PI's will practice consenting with research assistants and make sure the adequate skill level is obtained.

5.3 Study Evaluations/Data Analysis

Phase	Data Type	Source	Outcome	Analyses	Comment
1	Qualitative	Multidisciplinary providers, clinic staff, and Veterans	n/a	Grounded theory	Characterize screening information use in care
			management		
1	Quantitative	Patient	Pain-related disability, detection	By intervention arm*	At screening encounter

1&2	Quantitative	Patient, linked to VA health data for Veteran demographics and clinical factors	Pain missingness,	By intervention arm*	At screening encounter
2	Qualitative	Provider, patient	Satisfaction and experiences with screening including implementation	Grounded theory	Characterize experiences with the tablet and enhanced pain screening approaches

Outcome	Measure	Analysis	Model
Immediate pain related disability	NHIS pain-related disability	Arm 1,2,3 pairwise	Linear regression, adjusted for patient factors
Immediate pain missingness	NRS (nurse), NRS (tablet), PEG (tablet);	% missing pain ratings (Arm 1,2,3)	Logistic regression, adjusted for patient, rater (tablet perception), and environmental factors

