Effective Screening for Pain Study

NCT01816763

July 2018

Abstract

Objectives: The overall objective of our mixed method study is to evaluate a strategy to improve the quality and clinical usefulness of ‘the 5th Vital Sign’ in VA primary care. We will formatively evaluate experiences with and implementation of the *enhanced pain screening approaches* (patient self administered computer aided) including clinician perspectives on the use of pain screening to guide management. Our specific aims are to:

Aim 1. Characterize primary care team and Veteran patient perspectives on enhanced pain screening approaches compared with usual pain screening re., clinical usefulness and how to use skills, roles, and tasks of multidisciplinary clinicians and consultants to optimize pain care. Interviews and focus groups will inform development of the screening interface. **Aim 2.** Evaluate in a three-arm RCT the effects of enhanced pain screening approaches using the PEG (Arm 1), the ‘NRS pain now (Arm 2), compared with DVPRS (Arm 3) followed by usual clinician-assessed pain screening, on the detection of patient pain as well as feasibility, acceptability, and experiences with (e.g., pain missingness), patient-reported tablet-based pain assessment using quantitative patient screening outcomes, and interviews with patients, clinic, and facility staff **Research Plan:** At three sites (VA GLA, Minneapolis, and Portland) we will conduct interviews and focus groups with primary care staff about their experiences with pain screening and how to link screening to management in order to inform development of an integrated enhanced pain screening approach (using PEG and NRS now and DVPRS) on a touchscreen together with survey questions on risk for under-assessed or under-treated pain. The integrated protocol will be installed on a touchscreen tablet to use in a 3 arm RCT to evaluate the optimal approach to pain screening, along with an evaluation of the implementation experience.

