The 1 page field log will contain both identifiable (i.e., Full Name, last 4 digits of SSN, and contact information as needed for participation in follow up interviews) and unidentifiable data (i.e., participation status, participant ID, and observable demographics when necessary, and other research pertinent information). While in the clinic field logs will be kept on person by research staff and in a locking carrying case or secured mail bag to be transferred to a designated office. The paper documents will be stored in a locked filing cabinet inside of a locked office on VA campuses at the designated VA sites (i.e., Palo Alto, Minneapolis, Portland). A designated research assistant from each site will input the data into an encrypted and password protected Excel sheet that is kept on a secured server at VA Palo Alto. The designated research assistants at VA Portland VA Minneapolis will only have access to the cross-walk Excel sheet for their specific site. Research assistants from Palo Alto (i.e., [name] and [name]) will have access to a site specific Palo Alto Excel sheet and a master cross-walk Excel sheet that is populated by site specific crosswalks. Drs. [name] and [name] will have view only access to the master cross-walk excel sheet. At a later stage in the study, a designated programmer will have view only access to the master cross-walk excel sheet in order to compile data from both tablet survey data and medical records.

5. Tablet based survey content:

We will focus on content that is not available in existing VA administrative database the survey will include (not in this order):

- 1) an **introductory screen** which allow for registration using the unique participant number, and
- 2) **an algorithm corresponding to the three intervention arms of the RCT** and an underlying randomization engine to allocate Veterans to the three arms using a random number generator, with the corresponding pain screening measures (PEG, NRS one week, and DVPRS), and
- 3) The **Graded Chronic Pain Scale** (the gold standard for comparison),and
- 4) **Self-assessed level of physical activity**, and
- 5) **expectations and unmet need for pain treatment and management**, and

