- 6) **familiarity and experience with technology and satisfaction with the rating experience** including whether the veteran has previously used a tablet and environmental context because these items reflect previous concepts salient to pain rating variation, and
- 7) **access to and experience with smart mobile technology**

Depending on the consideration of survey length which we will prioritize to keep the survey at approximately 10 minutes, we will consider including several other items that previous research have shown to be important in considering pain outcomes including duration of pain in the previous year and the physical location of pain. In order to minimize survey burden and in order to complete our planned analyses, we will consider using VA data (rather than participant responses to obtain information about BMI, comorbidity, copay exemption status). We will also ensure physical attributes of the tablet screen best accommodate visually impaired and other physically disabled veterans where possible.

At the conclusion of the study in order to assess the degree to which implementation succeeded and Veterans who were missed by the tablet based protocol, we will compare all Veteran patients of the clinic during the study interval, as well as all Veterans who were approached but declined, with all Veteran users of the tablet during the same time by age, race / ethnicity, gender, cognitive impairment and mental health diagnoses, and NRS pain ratings, to assure that the tablet based screening process does not disadvantage any Veterans. We will gather these factors using VA electronic databases and will request a HIPAA authorization and waiver of documentation of informed consent for this portion of the study.

The usual care arm nursing staff rating of the 'NRS pain now' will be collected by linking the encounter to the Vital Signs Package to obtain the pain rating. Veterans' health records accessed in Corporate Data Warehouse and CAPRI/ VistAWeb/CPRS, will inform basic demographics and clinical factors in order to allow us to minimize the burden of the tablet protocol.

B. Patient Follow up Interviews:

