In order to learn about the experiences of Veterans with the pain screening via tablet and their experiences with the treatment of their pain, we will conduct up to 40 telephone interviews with Veterans after they have completed the tablet based survey. Patient interviews will take approximately 25-45 minutes. The interview will be audio recorded using VA approved recording devices (e.g., Olympus WS 822 or similar approved device), and transcribed by an external, VA-contracted Transcription Service.

1. Recruitment and Consenting:

In general, after Veterans complete the tablet-based survey, research staff will ask if it would be okay for us to contact them if we have follow up questions regarding their experience with using the tablet for pain screening. Not all Veterans will be contacted. A quota sampling technique will be used to ensure we interview a comparable number of Veterans who reported relatively high pain and Veterans who reported relatively low pain.

a. Participant Eligibility:

Veterans are eligible to participate in the interview portion of the study if they have completed the tablet based pain screening survey.

b. Recruitment:

Upon completion of the tablet based survey in the primary care clinics, the research associate will ask the Veteran if it would be okay for research staff to contact them via telephone within a few weeks if we have any follow up questions regarding their experience with using the tablet. If necessary, additional contact information will be collected and recorded on the Field Log. Of the Veterans that give us approval to contact them for follow up questions, a quota sampling approach will be used to ensure we

select a comparable number of Veterans who reported relatively high pain and Veterans who reported relatively low pain. If the Veteran is selected to participate in the follow-up interview, a research staff member will contact the veteran via telephone to complete the verbal consent process and the interview or to schedule a later time to complete the verbal consent process and interview..

2. Consent Process:

Prior to the interview, a research staff member will verbally consent the participant. We have approval for a waiver of documentation of informed consent. Date of consent and person obtaining consent will be logged on the secured Excel sheets stored on VA Palo Alto Servers.

3. Data Collection Procedures:

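### Section 5.3 gives the tablet satisfaction item no by-arm analysis, so among Aim 2's feasibility and acceptability outcomes only missingness is compared across the randomised arms

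*Protocol*

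**What the plan says.** The Protocol's abstract, under Aim 2, sets the RCT to evaluate the effects of the screening approaches "on the detection of patient pain as well as feasibility, acceptability, and experiences with (e.g., pain missingness"), and names two sources of evidence: "using quantitative patient screening outcomes, and interviews with patients, clinic, and facility staff".

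Section 5.1 (Phase 2, part A.5, tablet survey content) says "the survey will include (not in this order") a numbered list. Item 2 is the randomisation engine and the arm-specific pain measures. Item 6 covers "familiarity and experience with technology and satisfaction with the rating experience". The reason given for item 6 is that such concepts have been linked to variation in pain ratings.

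Section 5.3 lists satisfaction once: "Satisfaction and experiences with screening including implementation", data type qualitative, source provider and patient, analysis grounded theory. The two quantitative patient rows (pain-related disability and detection; missingness) are marked for analysis by intervention arm, and the satisfaction row is not. The model table has two outcomes, disability and missingness. The missingness measures are the nurse NRS, tablet NRS and tablet PEG. The nearest thing to satisfaction is a tablet-perception term among the adjustment factors for missingness. Table 1 (end of section 5.1), which lists outcomes for the arm comparisons, does not include satisfaction.

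Section 5.1 (Phase 2, part B) says "we will conduct up to 40 telephone interviews with Veterans after they have completed the tablet based survey". Interviewees must have completed the survey and agreed to be contacted. Quotas balance high and low reported pain; arm is not mentioned.

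**The concern.** Aim 2 asks for effects of the screeners, within a randomised trial, on how acceptable the assessment is to patients and how they experience it. A satisfaction question put to every randomised tablet user is the most direct quantitative evidence on this, and the randomisation makes a comparison across arms unconfounded. Section 5.3 sends satisfaction to a method that describes experience and does not estimate differences.

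The protocol also says that it will help select an optimal measure and inform national VA implementation. If a report then states that patients find the PEG, the NRS or the DVPRS more acceptable, the plan as written gives that statement only a small interview sample, chosen after randomisation. The randomised comparison would be left unmade although its data are in hand.

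**Working it through.** **1. Aim 2's outcomes set against section 5.3**

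| Item | Collected in the randomised sample? | Analysis in 5.3 |
|---|---|---|
| Missingness (Aim 2's own example) | Yes | By arm, logistic regression; measure list omits the DVPRS |
| Satisfaction with the rating experience (tablet item) | Yes, numbered survey content | None as an outcome |
| Satisfaction and experiences (qualitative row) | Patient interviews in a subset of at most 40; provider interviews | Grounded theory, no arm comparison |

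**2. Timing of the item.** The survey list is expressly unordered, so the protocol does not state that the item follows randomisation. It is a sound inference: satisfaction with a rating can be asked only after the rating, and the measure used for the rating is set by the allocation.

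**3. What a by-arm analysis would deliver.** The protocol gives no alpha, power, effect size or response format for this item, so there is no stated figure to reproduce. The numbers below show scale only.

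Inputs from the protocol: about 650 participants (section 5.1, Phase 2, part A.1); 1:1:1 allocation (abstract); up to 40 patient interviews (part B). Assumed: a binary satisfied / not satisfied item with 70%, 80% or 90% satisfied in both arms; two-sided 5%; 80% power for the score version.

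Per arm: 650 / 3 = 216.7. For the interviews, if they happened to divide evenly: 40 / 3 = 13.3.

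Half-width of the 95% CI for a pairwise difference = 1.96 × √(2p(1 − p) / n).

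- p = 0.8, n = 216.7: 1.96 × √(0.32 / 216.7) = 0.075, or 7.5 points.
- p = 0.7: 1.96 × √(0.42 / 216.7) = 0.086, or 8.6 points.
- p = 0.9: 1.96 × √(0.18 / 216.7) = 0.056, or 5.6 points.
- n = 13.3: 30.4 points at p = 0.8, 34.8 at 0.7 and 22.8 at 0.9.

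If the item is scored, the detectable standardised difference = (1.96 + 0.84) × √(2 / n).

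- n = 216.7: 2.80 × 0.096 = 0.27 SD.
- n = 13.3: 2.80 × 0.387 = 1.08 SD, or about 1.1 SD.

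The interview figures do not criticise the interviews, which were never planned as an arm contrast. They show only that the interviews could not stand in for one, even with an even split that the quotas do not provide for.

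**4. Whether missingness covers the same ground.** Only in part. Hypothesis 2b expects missingness to be equally low and sets enhanced screening against usual assessment, not one screener against another. The measure list omits one of the three randomised screeners. A Veteran can also answer every item and still dislike the instrument.

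**The case against.** A reader might infer that acceptability gets no randomised comparison at all. The documents do not support that. Aim 2 gives missingness as its example for this group of outcomes, and section 5.3 compares missingness across Arms 1, 2 and 3.

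Other arguments for the plan have weight:

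- Aim 2's wording on acceptability attaches to tablet-based assessment, which all three arms share, so it can be read as being about mode and not about the choice of screener. The sentence as a whole still sets out effects evaluated in a three-arm trial, so an arm comparison is a fair reading, though not the only one.
- No hypothesis in section 3.0 concerns satisfaction by arm. Its text on experience asks Veterans and staff to describe it, and a qualitative analysis suits that. This stands, and it limits the importance of the point.
- The tablet item is justified as a factor behind rating variation, so using it as a covariate is a deliberate choice. This also stands, but it does not prevent the item from serving as an outcome.
- The protocol never says that it will rank the screeners on acceptability, and its example of patient centredness is the inclusion of function. The risk of a weakly supported ranking is therefore conditional on someone making that statement.
- A statistical analysis plan, not shown here, could add the analysis. Silence in the protocol would then be no finding. But section 5.3 is not silent: it assigns satisfaction a data type and a method, and that method cannot give the arm effect that Aim 2 names.

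**Conclusion.** The point holds in a narrow form. Among Aim 2's feasibility, acceptability and experience outcomes, section 5.3 compares only missingness by arm, and with an incomplete measure list. Satisfaction is assigned to grounded theory, and the tablet satisfaction item has no by-arm analysis. The interviews describe experience and cannot estimate a difference between screeners.

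A by-arm estimate from the full sample would be reasonably precise: a half-width of about 6 to 9 points for a pairwise difference. This rests on 650 Veterans split evenly, complete answers, a binary item and an assumed 70% to 90% satisfied. Non-response would widen it.

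This is a worthwhile, inexpensive improvement. It leaves the stated hypotheses and existing models as they are, and it does not invalidate the trial's main comparison.

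**What to change.** Add one row to the model table in section 5.3:

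- **Outcome:** "satisfaction with the rating experience" (tablet item), designated secondary.
- **Population:** all randomised Veterans, analysed as allocated.
- **Analysis:** Arm 1, 2, 3 pairwise differences with 95% CIs, and the number giving no answer in each arm.
- **Model:** linear or proportional-odds regression, according to the response format, adjusted only for pre-randomisation patient factors. Perceptions recorded after allocation should stay out of this model, because the arm may affect them.
- **Reporting:** as an estimate, not a confirmatory test.

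Add the DVPRS to the missingness measure list, so that the one acceptability-related arm comparison already planned covers all three screeners. Keep the interviews to explain the results, and state that any claim that one screener is more acceptable to patients will rest on the randomised comparison.

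The cost is a few lines of text and one more regression on data already being collected. The downside is one more secondary outcome to report.

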2.0 Introduction

Despite the importance of pain and widespread interest in patient-centeredness, the VA remains exceptional in emphasizing and successfully making pain and its management a routine feature of the health record and a focus of care. Awareness of pain and efforts to improve pain management rest on the VA's '5th Vital Sign' – a policy and practice of nursing staff routinely screening for 'pain now' at every health encounter using a 0-10 Numeric Rating Scale (NRS) (1).

Our team's previous research on the VA's '5th Vital Sign' informs the specific design of the ESP study as well as the proposed research products. (5-7) Our evaluation of routine pain screening practice in the VA identified some important concerns that keep the VA's '5th Vital Sign' from living up to its full promise:

- The "fifth vital sign" measure of current pain intensity, demonstrates limited accuracy leading to only moderate correspondence (e.g., ROC of 0.76-0.8 in two studies) for chronic disabling pain measured with the Brief Pain Inventory (BPI) (5,10), and
- Nursing staff who deliver pain assessment in about 50% of cases use informal, unstructured pain queries (e.g., 'Is your knee good today?') rather than adhering to formal use of the 0-10 NRS leading to pain underestimation, despite efforts to standardize assessment (5), and
- Linkage is missing between the current pain screening approach and improved care—pain screening information is passively available but seldom used by busy providers who act on moderate to severe pain with augmented management in only about 15% of cases. (6,7)

Several alternatives to the current pain screening approach (e.g., nurse administered 'NRS pain now' improve the sensitivity and specificity of screening for chronic pain – the optimal measure being a three item scale incorporating intensity and emotional and physical interference (e.g., the PEG). (6,7) The PEG includes items that assess physical and emotional interference, and it is very similar to the gold standard BPI from which it is derived in sensitivity, specificity, and sensitivity to change in detecting clinically important, functionally impairing pain. (6)

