3.0 Objectives

The overall objective of our mixed method study is to evaluate a strategy to improve the quality and clinical usefulness of 'the 5th Vital Sign' in VA primary care. We will first develop a patient-self administered computer-aided pain assessment, then evaluate and refine the assessment using human-computer interaction laboratory usability testing. Next we will conduct a three site randomized controlled trial (RCT) to test a computer-based pain assessment protocol compared with usual pain screening. In the RCT we will evaluate three arms – one arm will use the PEG, a more sensitive screener including pain functional impairment, and a second arm will replicate the 'NRS now' allowing a direct comparison of patient-administered assessment vs. clinician assessed pain and a third arm will test the NRS at one week. All subjects will be screened with the '5th Vital Sign'. (allowing a three arm comparison of each of two computer based approaches vs. usual practice) Our specific aims are to:

Aim 1. Characterize primary care team perspectives on enhanced pain screening approaches compared with usual pain screening, including clinical usefulness and how to use skills, roles, and tasks of multidisciplinary primary care clinicians and consultants to optimize pain care. Additionally, we will try to understand Veterans' experiences with pain screening, assessment, and management (including use of opioid analgesics) in order to better link their actual experience with provider assessment and management practices. Interviews and focus groups will inform refinement of the items and screening interface; we will evaluate the interface including the PEG and 'NRS now' and the control arm for usability including among disabled veterans and for use in primary care.

Aim 2. Evaluate in a three-arm RCT the effects of enhanced pain screening approaches using a tablet and comparing the PEG, the 'NRS pain now', and usual clinician-assessed pain screening.

Hypothesis 2a: One of three enhanced pain screening approaches using the PEG, but not the 'NRS now' will be associated with improved detection of pain related disability **Hypothesis 2b:** Enhanced pain screening approaches vs. usual pain assessment will be associated with equally low missingness, Veterans, providers, and clinic and facility staff will characterize their experience with the enhanced screening protocol and important barriers, facilitators, and practical steps to inform implementation

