In general, we will solicit a visit-based sample of Veterans at each site so that we can ensure diversity in the population of Veterans and to minimize biases in our recruitment procedures. We plan to enroll approximately 650 participants among all three sites combined. We will recruit no more than 2000 respondents.

After a brief run-in phase, patients presenting in specified primary care clinics in the Palo Alto, Portland, and Minneapolis VAs will be asked to complete the survey on a tablet before vital signs are taken by clinic staff.

a. Participant Eligibility:

Veterans are eligible if they are attending a clinic visit in a participating primary care clinic and will have their vital signs taken as part of that visit and are not otherwise determined to be ineligible.

Veterans would be determined ineligible if they are:

- Severely visually impaired
- Incapable of rationale responses
- Physically unable to manipulate/control the tablet (unless a proxy is present and willing to input the Veteran's responses)

b. Recruitment

The primary recruitment will take place in the primary care clinics by trained research assistants approaching Veterans after they have checked in for their appointment. If a veteran expresses interest in participating, they will be informed of the study and screened for eligibility. All veterans approached by clinic staff will receive an anonymous study identification. Research staff will recruit in clinics for full or half-days selected from within the study enrollment window. A Research Assistants will use a 'Next Available' method of randomizing which Veterans will be approached (i.e., When the R.A. is ready to begin/resume recruitment the next patient that completes the check in process for the clinic will be approached.)

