If possible, research staff will attend a local clinic staff meeting to briefly inform the staff of the study. By partnering with local clinic leadership, we plan to send emailed invitations to eligible staff members. A log of all contact attempts will be maintained and after a maximum of 3 contact attempts the staff member will be removed from the contact list.

2. Consent Process:

Prior to the interview, a research staff member will verbally consent the participant. We have approval for a waiver of documentation of informed consent. Date of consent and person obtaining consent will be logged on the secured Excel sheets stored on VA Palo Alto Servers.

3. Data Collection Procedures:

We will conduct up to 40 telephone interviews that will take approximately 20-30 minutes. The interviews will be audio recorded and later transcribed by a VA contracted transcription service. For interview questions/content please see the Provider Interview Protocol.

4. Data Security:

Any information linking identifiable information with an assigned participant ID will be located on the secured Excel sheets. These Excel sheets will be secured and stored as previously mentioned under Phase 2: a: Data Security.

Audio files will be uploaded to the secured server located at VA Palo Alto. The audio Files will be saved using the assigned participant id. Audio files and de-identified transcripts will be transferred between VA servers and the transcriptions service via an approved secured FTP server.

Figure 1: Estimated enrollment scheme for ESP

Due to randomization the proposed enrollment algorithm will allow analytic comparison of each assessment measure / mode to the other. The table below specifies the Arm to Arm comparisons but the outcomes of each comparison are ‘clinically significant pain’ defined as pain that is moderate to severe, pain that is associated with disability, or unmet need for additional management.

Main comparison (s) of interest		Arm (s)	Comment
1	Tablet: PEG vs. NRS 1 week vs. DVPRS	1 to 2 to 3 tablet comparison	Baseline arm to arm difference

Table 1: Main analytic comparisons by screening measure and mode for outcomes of detection of pain, detection of moderate / severe pain (clinically relevant), pain associated with disability and unmet needs for treatment

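### The section 5.3 row for Hypothesis 2a names an NHIS measure absent from the listed survey content, omits the declared gold standard, and uses a regression on arm that cannot measure detection

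*Protocol*

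**What the plan says.** **Hypothesis.** Protocol section 3.0, Hypothesis 2a, predicts that screening with the PEG, but not the current-pain NRS, "will be associated with improved detection of pain related disability".

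**Analysis.** Section 5.3 has two tables.
- The first lists pain-related disability and detection as an outcome. Its source is the patient, it is analysed by arm, and it is timed at the screening encounter. No instrument is named.
- The second is the only place that gives a measure and a model. The measure is "NHIS pain-related disability", the contrast is pairwise between the three arms, and the model is "Linear regression, adjusted for patient factors".

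**Data collection.** Section 5.1, Phase 2 A.5, lists seven kinds of tablet content. Item 3 is the Graded Chronic Pain Scale, described as "the gold standard for comparison". No item is an NHIS measure. The list is not closed, since "we will consider including several other items that previous research have shown to be important in considering pain outcomes", but the only examples are pain duration and pain location. Linked VA records are described as supplying the nurse's pain rating, demographics and clinical factors.

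**Main comparisons.** Table 1 in section 5.1 refers to "pain associated with disability and unmet needs for treatment" without naming an instrument.

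**The concern.** There are two faults in one table row.

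1. **Instrument.** The measure to be analysed is not among the listed data, and the scale declared as the reference standard is not analysed. A reader cannot tell which instrument Hypothesis 2a is to be judged against.
2. **Model.** Hypothesis 2a is about detection, that is, how well a screener's result agrees with a reference measure of disability. A regression of disability on arm asks whether one arm is more disabled than another. Randomisation makes the expected answer no, whichever screener is better.

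Correcting the instrument name alone would therefore leave the hypothesis untestable. A null result would say nothing against the PEG. A significant one would reflect chance imbalance, or at most an effect of question order, and neither is detection. The trial is meant to inform the national choice of a pain screening measure.

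**Working it through.** **Step 1. Set the sections side by side.**

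| Place in Protocol | Disability instrument | Statistic |
|---|---|---|
| 3.0, Hypothesis 2a | none named | detection |
| 5.1, tablet content | Graded Chronic Pain Scale, as gold standard | none |
| 5.1, Table 1 | none named | detection, compared between arms |
| 5.3, first table | none named (source: patient) | by arm |
| 5.3, second table | NHIS measure | pairwise linear regression |
| 9.0 | NHIS, reference entry 38 only | not applicable |

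The Graded Chronic Pain Scale and the NHIS measure never appear in the same place. No row relates a screener score to a reference standard.

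**Step 2. What the stated model estimates.** Let D be the disability score and A the arm. The regression is D = α + β·A + (patient factors) + error. Allocation is random, and the arm changes only which screening questions are asked in the same session. So E[D | arm 1] = E[D | arm 2], and β = 0 in expectation. The screener score S does not enter the model. Detection depends on S given D, for example AUC = P(S in a disabled patient > S in a non-disabled patient). Adjusting for patient factors does not change this.

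**Step 3. Inputs for a numerical check.** The Protocol gives no effect size or power figure for this outcome, so there is none to reproduce.
- Size: section 5.1 states "We plan to enroll approximately 650 participants among all three sites combined", allocated 1:1:1. 650/3 = 216.7, about 217 per arm.
- Lower AUC, 0.76 to 0.80: section 2.0 reports "ROC of 0.76-0.8 in two studies". That figure is for the existing nurse screen against the Brief Pain Inventory, so it serves only as an anchor.
- Assumed, not in the Protocol: higher AUC 0.85 to 0.90; disability prevalence 20%, 30% or 50%.

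**Step 4. Simulation.** Two arms, 4,000 trials per setting, two-sided 5%. The disability score is N(0,1) in both arms, and the disabled are the top 20%, 30% or 50%. The screener score is binormal with the given AUC (mean shift √2·Φ⁻¹(AUC)). Test A is the unadjusted regression of disability on arm. Test B is z = (AUC₁ − AUC₂)/√(V₁ + V₂), with DeLong variances.

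| AUCs | A: % significant at prevalence 20/30/50% | B: % significant at prevalence 20/30/50% |
|---|---|---|
| 0.85 vs 0.76 | 5.2 / 4.4 / 5.1 | 41 / 51 / 60 |
| 0.90 vs 0.76 | 5.2 / 5.0 / 5.5 | 83 / 92 / 96 |
| 0.90 vs 0.80 | 5.2 / 5.3 / 5.4 | 61 / 73 / 80 |
| 0.85 vs 0.80 | 5.1 / 5.3 / 5.6 | 18 / 21 / 25 |
| 0.80 vs 0.80 | – | 5.5 / 5.0 / 4.4 |

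The simulation error around a true 5% is 1.96·√(0.05·0.95/4000) = 0.7 percentage points, so 4.3% to 5.7% is what chance gives. All Test A results lie inside that range, and Test B holds its level when the AUCs are equal.

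**Step 5. Sensitivity to the set-up.** A second simulation used 216 per arm, 2,000 trials per setting and prevalence 20% to 40%. Disability scores had mean 6 in the disabled, mean 2 in the others, and SD 2. The mean arm difference in disability stayed between −0.015 and 0.007 points. The regression was significant in 4.2% to 5.6% of trials, both for equal AUCs (0.78) and for 0.90 vs 0.76. The AUC comparison for 0.90 vs 0.76 was significant in 84% to 96%.

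**The case against.** - **A source is given.** The first 5.3 table names the patient as source, and the survey list leaves room for more items. This stands as far as it goes: the NHIS measure is unlisted rather than excluded. But a generic source supplies no NHIS item, and the gold standard still has no analysis.
- **The row is brief and the SAP may hold the full model.** A regression relating screener score to disability, compared between arms, is not expressly ruled out. The row does not say this, however. It names an outcome, an arm contrast and a model. An SAP that follows it inherits the fault, and one that departs from it contradicts the Protocol.
- **Text may have been lost.** The by-arm cells in the first 5.3 table carry an asterisk with no visible note. That is a fair caution about that table, but the measure and model stand in the other one.
- **The intent to assess performance is stated.** The consent section and Table 1 both point that way. This supports the concern, because the model row does not carry the intent out.
- **The power figures do not describe this trial.** Largely true: the AUCs and prevalence are illustrative, and the 0.76 to 0.80 anchor comes from a different screener and reference. The zero expected arm effect needs none of them.
- **A between-arm comparison does not test tablet against usual screening, and the arm labels for the NRS differ between sections.** Both are true, and both are separate matters. Table 1's main comparison is arm to arm, and the repair below serves that.

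**Conclusion.** The concern holds, and the row must be corrected before the analysis. The instrument conflict is plain from the text. The fault in the model follows from randomisation, with the disability measure taken in the same session as the screener and question-order effects set aside. Read as written, the regression has power equal to its significance level for Hypothesis 2a: 4.4% to 5.6% in simulation, whatever the screeners' accuracy. The 18% to 96% power of an AUC comparison is illustrative and rests on the assumed higher AUC, the assumed prevalence and binormal scores.

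**What to change.** In the second table of section 5.3:

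1. Replace the NHIS entry with the Graded Chronic Pain Scale and name it as the reference standard for Hypothesis 2a. If the NHIS measure is intended, add its items to the tablet content list and state which instrument governs the hypothesis.
2. Replace the linear regression on arm with a pairwise between-arm comparison of how well each screener detects disability on that reference, for example AUC, with sensitivity and specificity by arm.

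**Cost.** One table row and a little more analysis. No new data are needed with the Graded Chronic Pain Scale; NHIS items would have to fit a survey of about 10 minutes. The Protocol should also acknowledge that a detection comparison of this size has limited power for small differences: 18% to 25% for AUC 0.85 vs 0.80 at about 217 per arm, under the assumptions above.
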